8.7.2. Intracranial hemorrhage detection accuracy

Endpoint (2nd Secondary endpoint)

Accuracy of DE-CBCT to determine the presence of intracranial hemorrhage using neCT as the reference standard.

Applicable subjects

All subjects in the study.

Data

- Intracranial hemorrhage
 - Yes / No

Analysis

Images are evaluated by radiologists using neCT as reference standard and the hemorrhage detection accuracy is defined.

Hypothesis:

$$\begin{aligned} H_0: \pi_3 &\leq 0.80 \\ H_1: \pi_3 &> 0.80 \end{aligned}$$

Where π_3 is the observed intracranial hemorrhage accuracy and 0.80 is the performance goal.

8.8. Additional Objectives – 3D diagnostic imaging

8.8.1. Ischemic stroke diagnostic accuracy, vessel tree visibility and hemorrhage detection accuracy compared to regular CBCT

Applicable subjects, data and analysis same to that of primary and secondary endpoints, but using conventional CBCT image data (acquired from the top layer of the investigational device) as reference.

IGT Systems	Clinical Research Protocol Next Generation X-ray Imaging System (NEXIS)	Doc ID: XCY612-130814 Rev: 01 Page 37 of 57
-------------	----------------------------------------------------------------------------	---------------------------------------------------

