5.3. Additional objectives – 3D diagnostic imaging

- Ischemic stroke diagnostic accuracy, vessel tree visibility and hemorrhage detection accuracy compared to regular CBCT.
- Characterization of brain tissue as normally perfused, at risk (penumbra) or infarcted.
- Characterization of intracranial hemorrhage.
- Characterization of intracranial thrombus.
- Separation of grey and white matter, and iodine from blood and calcium.
- Assessment of novel segmentation and reconstruction techniques.

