6.5. Investigational device exposure and comparators

As per clinic standard, patients with suspected ischemic stroke are evaluated with neCT, mCTA and CTP upon admission. Patients arriving from another hospital with a confirmed LVO can optionally be imaged with only neCT and CTP. Also, as per clinic standard, ischemic stroke patients treated in any way (thrombolysis and/or thrombectomy) undergoes DECT 12-36 hours after treatment to assess the presence and extent of hemorrhage and ischemia. Patients diagnosed with hemorrhagic stroke will typically be evaluated with neCT and mCTA/CTA upon admission.

This study will investigate the performance of DE-CBCT in comparison to regular neCT/mCTA/CTA/CTP imaging at admission and subsequent DECT (DECT only for subjects in 3.I and 3.II). Table 3 provides an overview of the devices each subject is exposed to depending on inclusion criterion.

IGT Systems	Clinical Research Protocol	Doc ID: XCY612-130814 Rev: 01 Page 26 of 57
	Next Generation X-ray Imaging System (NEXIS)	

	Day 1	Day 2						
Inclusion criterion	Standard imaging (CT-based)	Iodine contrast eligibility test	DE-CBCT w/o contrast agent	DE-CBCT w contrast agent	Iodine contrast eligibility test	Standard imaging (DECT)	DE-CBCT w/o contrast agent	DE-CBCT w contrast agent
3.I	X	X	X	X ¹	X	X ²	X	X ¹
3.II	X				X	X	X	X ¹
3.III	X	X	X	X ¹				

Table 3. Overview of the devices the subject is exposed to depending on inclusion criterion. Timeline: left to right.

¹ No iodine contrast agent will be administered if deemed ineligible

² Only if subject has been treated with thrombolysis

Italics depicts standard diagnostic protocol

Subjects presenting with acute stroke will be evaluated by the physician in accordance with the institutional practice, to establish an appropriate treatment plan based on the subject's medical condition and available diagnostic screening procedures prior to recruitment in the Study. The 3rd inclusion criterion will define the investigational device exposure for the subjects:

3.I subjects will be imaged with DE-CBCT without and with contrast agent day 1 after standard diagnostic CT imaging. If subject is still hospitalized at Karolinska on day 2, an additional DE-CBCT without and with contrast agent will be made.

3.II subjects will be imaged with DE-CBCT without and with contrast agent day 2 directly after their standard diagnostic DECT scan.

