8.1. Image data management

The raw image data with added dual energy properties (DE-CBCT) will be processed using novel reconstruction and segmentation techniques. During the intervention only the product reconstruction algorithm is available for raw image data acquired by the first layer of the detector and images reconstructed in this fashion will be identical to current CBCT.

After the intervention the DE-CBCT raw image data will be reconstructed with the novel spectral reconstruction software and then evaluated by three independent neuroradiologists (not involved in the clinical investigation) for subjective outcome variables. The first cases will also be used to iterate and optimize reconstruction algorithms. Images will be processed on-site and off-site. For ordinal outcome variables comparing the subjective performance of DE-CBCT and CBCT to CT, CTA and CTP (such as the first secondary objective), neuroradiologists will have access to both DE-CBCT and reference image data concurrently. For the primary and second secondary objective DE-CBCT and reference image, data will be cleaned from any information regarding acquisition technique and evaluated randomly and separated in time, in order to limit the possibility of bias.

A secure image data repository will be set up at Karolinska University Hospital, the access to which will be provided through IntelliSpace Discovery (ISD) that will serve as the interfacing client for managing and logging the access of data by authorized personnel involved in this study. No additional software will be required by the user to access the data as the ISD client runs in chrome web browser with a zero footprint i.e., no data will be stored on user's computer while using the ISD interface.

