8.3. Statistical methods

All variables will be summarized by descriptive statistics. The statistics for continuous variables includes mean, median, standard deviation, 95% confidence interval for the means, and the number of observations. For categorical variables, number of events, event rate, and 95% confidence interval for the event rate will be presented.

For categorical variables, the Fisher's Exact or chi-squared test will be used. For numerical variables, Student's t-test will be applied for image quality parameters such as signal-to-noise ratio (SNR) and contrast-to-noise ratio (CNR). For ordinal rank variables concerning radiologist interpretation, the Wilcoxon test will be used. The decision to use non-parametric or parametric tests will be based on the result from Shapiro-Wilk test as well as the distribution of the data on a P-P plot.

Receiver operating characteristic (ROC) curves will be constructed and accuracy as well as area under the curve (AUC) will be used to assess image diagnostic performance, where applicable. Sensitivity, specificity, negative and positive predictive value will be assessed with optimal cut off, where applicable. The DeLong test will be applied when comparing ROC curves. The Kappa coefficient will be used to evaluate interrater and within-observer agreement, where applicable. Additional statistical methods may be used in accordance with relevant literature (33). A biostatistician is involved in planning and executing the statistical analyses.

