8.6. Primary objective

8.6.1. Ischemic stroke diagnostic accuracy

Endpoint

Accuracy of DE-CBCT ASPECTS to determine the extent and localization of ischemic stroke changes in brain tissue, using neCT ASPECTS as the reference standard.

Applicable subjects

Subjects diagnosed with ischemic stroke on CT.

Data

- ASPECTS
 - Left / Right
 - 1 to 10
 - Location - L, C, IC, I, M1, M2, M3, M4, M5, M6

Analysis

Images are evaluated by radiologists using neCT as reference standard and the ASPECTS diagnostic accuracy is defined.

Hypothesis:

$$H_0: \pi_1 \leq 0.80$$

$$H_1: \pi_1 > 0.80$$

Where π_1 is the observed ASPECTS accuracy and 0.80 is the performance goal.

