8.9. Additional Objectives – 3D image quality parameters

8.9.1. Objective image quality parameters

Applicable subjects

All subjects.

Data

HU (or equivalent), standard deviations, CNR and SNR

- Central vs peripheral location in the image
- Water

IGT Systems	Clinical Research Protocol Next Generation X-ray Imaging System (NEXIS)	Doc ID: XCY612-130814 Rev: 01 Page 39 of 57
-------------	----------------------------------------------------------------------------	---------------------------------------------------

- Fat
- Grey matter
- White matter
- Blood
- Iodine
- Calcium (bone)

Analysis

Absolute numerical variables, mean and standard deviations of image quality indexes will be compared to reference standards (CT, DECT, CBCT).

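### Section 8.8.1, read literally, scores DE-CBCT ASPECTS and hemorrhage calls against CBCT, so its figure is agreement between two techniques and cannot show which is more accurate

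*Combined protocol and SAP*

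**What the plan says.** Section 5.3 lists as an additional objective "Ischemic stroke diagnostic accuracy, vessel tree visibility and hemorrhage detection accuracy compared to regular CBCT". Section 8.8.1 is where the plan addresses it. Subjects, data and analysis are those of the primary and secondary endpoints, "but using conventional CBCT image data (acquired from the top layer of the investigational device) as reference".

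The two analyses at issue are proportions of correct calls against neCT:

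- ASPECTS, by region (8.6.1): "Images are evaluated by radiologists using neCT as reference standard and the ASPECTS diagnostic accuracy is defined".
- Hemorrhage, yes or no per subject (8.7.2): "Images are evaluated by radiologists using neCT as reference standard and the hemorrhage detection accuracy is defined".

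Three other places bear on the question:

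- Section 8.1 sets DE-CBCT and CBCT against CT, but only "For ordinal outcome variables comparing the subjective performance of DE-CBCT and CBCT to CT, CTA and CTP". For the primary and second secondary objectives it asks for reads stripped of acquisition information, in random order and separated in time. It does not say how CBCT is read.
- Section 8.3 says "The DeLong test will be applied when comparing ROC curves", without assigning that test to any endpoint.
- Section 8.9.1 says "image quality indexes will be compared to reference standards (CT, DECT, CBCT"), which uses the term reference standard for what are simply comparators.

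**The concern.** An accuracy needs a standard taken as true. If CBCT takes the place of neCT, a DE-CBCT call counts as correct when it matches CBCT. A CBCT error that DE-CBCT corrects then counts against DE-CBCT, and a perfect DE-CBCT would score only CBCT's own accuracy. Section 2.8 says that flat panel systems lack detailed low-contrast discrimination, and Section 2.10 expects energy separation to improve tissue characterization. Corrected CBCT errors are therefore what the technique is meant to produce.

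At stake is whether this additional objective can say that dual energy is better or worse than regular CBCT for ischemic change and hemorrhage. Vessel visibility is outside the point, because its inferior/equal/superior rating carries direction.

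**Working it through.** **Inputs.** Section 8.2 gives ten ASPECTS regions per subject, at least 14 ischemic subjects (140 regions), and 20 subjects for hemorrhage. The performance goal is 0.80, with one-sided alpha 0.025 (primary) and 0.0125 (secondary). Section 8.8.1 states no figure of its own. The documents give neither CBCT accuracy nor the overlap of errors, so the splits below are assumptions, with one binary read per item.

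**The plan's own figure.** For the primary endpoint the normal formula is n = [(1.96 × √(0.80 × 0.20) + 1.2816 × √(0.90 × 0.10)) / 0.10]² = 136.5, so 137. The exact binomial also first reaches 90% power at 137. The stated figure reproduces.

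**Algebra.** With binary calls, each disagreement means that exactly one technique is right. Let b be the number of items where only DE-CBCT is right, c the number where only CBCT is right, and n the number of items.

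- Agreement A = 1 − (b + c)/n
- Accuracy difference (DE-CBCT minus CBCT) = (b − c)/n

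Hence |difference| ≤ 1 − A, and exchanging b and c leaves A unchanged. The size is limited, but the sign is not identified.

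**ASPECTS, 140 regions: 112 right on both, 14 wrong on both, 14 discordant.** A = 126/140 = 0.90 throughout.

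| b, c | DE-CBCT | CBCT | Difference | 95% CI, no clustering | 95% CI, ICC 0.3 |
|---|---|---|---|---|---|
| 14, 0 | 0.90 | 0.80 | +0.10 | 0.050 to 0.150 | 0.004 to 0.196 |
| 7, 7 | 0.85 | 0.85 | 0 | −0.052 to 0.052 | −0.101 to 0.101 |
| 0, 14 | 0.80 | 0.90 | −0.10 | −0.150 to −0.050 | −0.196 to −0.004 |

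The intervals are what scoring both techniques against neCT would give. They use the paired Wald SE = √[(b + c) − (b − c)²/n]/n, multiplied by √(1 + 9 × ICC) for ten regions per subject. For the first row, √(14 − 1.4)/140 = 0.0254, and ×1.96 gives ±0.050. The ICC of 0.3 is assumed.

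**Hemorrhage, 20 subjects.** Agreement of 18/20 fits DE-CBCT 1.00 and CBCT 0.90, or the reverse.

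**A large true gain.** Take CBCT at 0.70 and DE-CBCT at 0.95. With independent errors A = 0.70 × 0.95 + 0.30 × 0.05 = 0.68. If DE-CBCT corrects CBCT errors and adds none, A = 1 − 0.25 = 0.75. Both values are unchanged if the two accuracies are swapped.

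**If the 0.80 goal and its alphas were carried over (the text leaves this unclear).** The smallest passing ASPECTS count is 122/140 (exact p = 0.0185), which still allows differences up to ±18/140 = ±0.13. For hemorrhage only 20/20 passes (0.80²⁰ = 0.0115), so one call that DE-CBCT corrects would fail the test.

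**The case against.** The strongest reply is that reference here just means comparator. Sections 8.9.1 to 8.10.1 use the term that way, and the heading of 8.8.1 speaks of a comparison with regular CBCT. This stands in part: it makes the intent uncertain. But a sentence that keeps the analysis and changes the reference most naturally puts CBCT in neCT's place, and on the looser reading no truth standard is named.

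A second reply is that Section 8.3 already plans DeLong tests, sensitivity and specificity. DeLong is not assigned to 8.8.1. Sensitivity and specificity taken against CBCT would show which technique calls more positives, not which is right.

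A reader might infer that the plan as a whole can never show direction. That goes too far. Let a be DE-CBCT accuracy against neCT on the same reads. When a exceeds A, CBCT accuracy is at most 1 + A − a, so the sign favours DE-CBCT whenever a > (1 + A)/2. With a = 0.90 and A = 0.75, CBCT lies between 0.65 and 0.85. With both at 0.90 it lies between 0.80 and 1.00, and the sign stays open. No such combination is planned, so the limit belongs to the 8.8.1 figure taken alone.

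The most substantial reply concerns the remedy. "3.II subjects will be imaged with DE-CBCT without and with contrast agent day 2 directly after their standard diagnostic DECT scan", while Section 6.5 places neCT at admission. A lesion that appears in between, seen on DE-CBCT and missed on CBCT, would be scored as a DE-CBCT error, so scoring against neCT could itself give the wrong sign. This stands and shapes the fix.

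**Conclusion.** The point holds for ASPECTS and hemorrhage on the literal reading of 8.8.1. The figure is agreement between two techniques from one acquisition. It limits the accuracy difference to ±(1 − A), for example ±0.10 at A = 0.90, and gives no direction. The algebra needs only binary calls; the accuracies, error splits and ICC are illustrative. Confidence is moderate, because the plan's loose use of reference leaves the intent open.

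A reader might infer that the primary or secondary conclusions are weakened. They are not: those endpoints keep neCT or CTA as reference. Nor does the text establish that the 0.80 goal applies to 8.8.1. This is an additional objective with no sample size of its own in a proof-of-concept study. The plan should be amended, but what is affected is the interpretation of that objective only.

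**What to change.** In 8.8.1, for ASPECTS and hemorrhage:

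- Score DE-CBCT and CBCT each against the same neCT reference reads, in the same subjects. State that CBCT is read masked and separately in time, as 8.1 requires for the primary and second secondary objectives. Combine the three readers by the same rule for both techniques.
- Report the paired accuracy difference with a 95% CI, clustered by subject for ASPECTS and McNemar-type for hemorrhage. State that the 0.80 goal does not apply.
- Base any directional statement on same-day pairs: day-1 scans of 3.I subjects for ASPECTS, and of 3.I and 3.III subjects for hemorrhage. Report 3.II subjects separately, because changes after admission neCT would penalise the more sensitive technique.
- Keep DE-CBCT/CBCT agreement as a descriptive figure, and leave the vessel visibility rating as it is.

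No extra scans are needed. CBCT comes from the same acquisition and must be read in any case, and neCT and DE-CBCT are already read for the main endpoints. If CBCT was to be read side by side with DE-CBCT, separate masked CBCT reads are added work.

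The price is precision. The plan does not give the split between 3.I and 3.II, and restricting to same-day pairs leaves fewer subjects. Two discordant hemorrhage calls, both favouring DE-CBCT, give an exact McNemar p of 0.50. Six, all one way, are needed to fall below 0.05 (2 × 0.5⁶ = 0.031). The result should stay descriptive.

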8.8.2. Characterization of brain tissue as normally perfused, at risk (penumbra) or infarcted

Applicable subjects

Subjects diagnosed with ischemic stroke.

Data

- mCTA collateral score
 - Side: Left / Right
 - Score: 1 to 5
- ASPECTS score - CBV, MTT, CBF, TTP, Tmax or exploratory measurements
 - Side: Left / Right
 - Score: 1 to 10
 - Location - L, C, IC, I, M1, M2, M3, M4, M5, M6
- Infarct, penumbra and normally perfused tissue
 - Volume segmentation in ml

Analysis

Images are evaluated by radiologists using mCTA or CTP as reference standard. This is an exploratory objective.

8.8.3. Characterization of intracranial hemorrhage

Applicable subjects

Subjects diagnosed with intracranial hemorrhage.

Data

Extraaxial or Intraaxial

- Extraaxial: SAH / SDH / EDH
 - Small, medium or extensive (SAH)
 - Maximum width (SDH/EDH)
- Intraaxial: Contusion/deep/lobar/cerebellum/brainstem/intraventricular
 - Volume segmentation in ml

Hemorrhagic transformation of ischemic stroke

- HI – HI1 or HI2
- PH – PH1 or PH2
- Iodine vs blood – Majority/Minority or Equal

Analysis

Images are evaluated by radiologists using CT and/or DECT as reference standard.

8.8.4. Characterization of intracranial thrombus

Applicable subjects

Subjects with an intracranial thrombus on CT.

Data

Localisation

- Side: Left / Right
- Localisation of thrombus: dICA, M1-M2, M3-M4, A1-A2
- Attenuation of thrombus (HU)
- Homogenous/heterogenous attenuation

IGT Systems	Clinical Research Protocol Next Generation X-ray Imaging System (NEXIS)	Doc ID: XCY612-130814 Rev: 01 Page 38 of 57
-------------	----------------------------------------------------------------------------	---------------------------------------------------

- Size: In mm as seen in maximum intensity projection (MIP)
 - Non contrast scan
 - Contrast enhanced scan (perceived filling defect)

Inferior, Equal or Superior

- Perceived ability to identify thrombus

Analysis

Images are evaluated by radiologists using CT and/or DECT as reference standard.

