2.11.2. Endovascular treatment

A blood clot/thrombus in a proximal intracranial artery can be removed by an endovascular procedure termed thrombectomy. The thrombectomy aims to achieve arterial recanalization and thus restoration of blood flow and oxygen delivery to brain tissue. Typically, the femoral artery is punctured with a needle and the intracranial arterial vasculature is subsequently accessed using a catheter system under X-ray guidance. Endovascular treatment for patients with AIS and LVO using second-generation devices (primarily stent retrievers (SRs)) have demonstrated to be beneficial across five large randomized clinical trials (RCTs) (6). The addition of endovascular thrombectomy to standard medical care also resulted in better 24-h recanalization rates (71% of successful recanalization rate)(6). In these five RCTs, mechanical thrombectomy was performed in more than 80% of cases with a SR, a self-expanding stent used to retrieve thrombi (6). These studies provided compelling evidence for the beneficial results of mechanical thrombectomy in patients with LVO of the anterior circulation presenting within 6 hours of symptom onset and has since 2015 been established practice world wide.

Furthermore, RCTs DAWN and DEFUSE 3 published in 2018 provided insights that thrombectomy can be a beneficial treatment option up to 24 hours after symptom onset, thus making endovascular recanalization a possible treatment option for an even larger patient group (8, 9). These studies both used “mismatch” concepts separating irreversible ischemic tissue from potentially salvageable tissue to select patients for thrombectomy.

IGT Systems	Clinical Research Protocol Next Generation X-ray Imaging System (NEXIS)	Doc ID: XCY612-130814 Rev: 01 Page 17 of 57
-------------	----------------------------------------------------------------------------	---------------------------------------------------

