Subjects not eligible for thrombectomy (criterion 3.I) receive less iodine contrast agent and radiation exposure compared to patients undergoing thrombectomy, where iodine is used to navigate during the procedure under X-ray image guidance. Investigational DE-CBCT of these subjects on day 1 imposes varying extent of residual iodine intracranially (from previous standard of care imaging). However, these subjects typically show very relevant imaging features, as hyperacute ischemic changes are challenging yet crucial to visualize. Moreover, DE-CBCT imaging potentially enables iodine removal/suppression. If still hospitalized day 2, an additional DE-CBCT enables diagnostic information about stroke progression.

Subjects that have undergone thrombectomy (inclusion criteria 3.II) will be included one day after admission (day 2), when most of the iodine typically has been filtered out by the kidneys. An absolute GFR (aGFR) and non-renal risk factors for CI-AKI will be assessed before administering iodine contrast agent. These measures will ensure that the risks associated with iodine contrast agents will be minimized.

Similar to above, subjects with a verified intracranial hemorrhage (inclusion criteria 3.III) will be imaged without and with iodine contrast agent day one after assessment of aGFR and non-renal risk factors.

If the subject is deemed inappropriate to receive iodine contrast agent, only imaging without iodine contrast agent will be done. In addition to above, other individual or healthcare aspects may select subjects to undergo only imaging without injection of iodine contrast agent.

6. Study Design

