8.8.6. Assessment of novel segmentation and reconstruction techniques

Applicable subjects

All subjects.

Data

- Separate, delineate infarcted and viable brain tissue
- Identify thrombus location
- Separate, delineate infarcted tissue from tissue at risk and normally perfused tissue

Analysis

This is an exploratory objective. Reference standards include commercially available CT segmentation software from concurrent CT.

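### Section 8.8.2 sets the post-thrombectomy DE-CBCT of 3.II subjects against admission perfusion imaging, and Section 8.8.4 does not say which day's scan is the thrombus reference

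*Combined protocol and SAP*

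**What the plan says.** Three additional objectives are involved.

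- **Section 8.8.2 (perfusion state).** Applicable subjects: "Subjects diagnosed with ischemic stroke", which takes in groups 3.I and 3.II. Data: mCTA collateral score, ASPECTS on perfusion maps, and volumes of infarct, penumbra and normally perfused tissue. Reference and status: "Images are evaluated by radiologists using mCTA or CTP as reference standard. This is an exploratory objective".
- **Section 8.8.4 (thrombus).** Applicable subjects: "Subjects with an intracranial thrombus on CT". Data: side, location, attenuation, homogeneity, size in mm, and an inferior/equal/superior rating of the ability to identify the thrombus. Reference: "Images are evaluated by radiologists using CT and/or DECT as reference standard". No time point is given.
- **Section 8.8.6 (segmentation and reconstruction).** All subjects, exploratory, with items on infarct, thrombus location and tissue at risk. "Reference standards include commercially available CT segmentation software from concurrent CT".

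The imaging schedule is in Section 6.5 and Table 3. Suspected ischemic stroke is imaged with neCT, mCTA and CTP on admission; transfers with a confirmed large vessel occlusion may have only neCT and CTP. The standard day-2 scan is DECT. Group 3.I has DE-CBCT on day 1, and again on day 2 if still in hospital. Group 3.II has DE-CBCT on day 2 only, directly after the DECT. Section 5.5 agrees: "Subjects that have undergone thrombectomy (inclusion criteria 3.II) will be included one day after admission (day 2"), the stated reason being iodine clearance.

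**The concern.** A comparison with a reference scan tells us about the device only if both scans image the same state. In 3.II, thrombectomy comes between the admission scans and the DE-CBCT, and Section 2.11.2 gives its aim as reopening the artery and restoring flow. Tissue that was penumbra on admission CTP may have been salvaged or have infarcted by day 2, and a clot seen on admission may be gone.

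If 3.II subjects are pooled with 3.I against admission imaging, such changes enter the results as disagreement between DE-CBCT and its reference. The more effective the thrombectomy, the worse the device would look. This is a first-in-man proof of concept, so the results on tissue viability and thrombus are likely to influence what is studied next.

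**Working it through.** The plan states no sample size, power or detection rate for Sections 8.8.2, 8.8.4 or 8.8.6, so there is no figure of its own to reproduce. The check sets the scan times side by side and adds one illustration.

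**Step 1. Pair each DE-CBCT with the scans available (Section 6.5, Table 3).**

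| DE-CBCT | Admission neCT/mCTA/CTP | Day-2 DECT |
|---|---|---|
| 3.I, day 1 | Same day, earlier | Not applicable |
| 3.I, day 2 (if still in hospital) | Previous day | Only if given thrombolysis |
| 3.II, day 2 | Before thrombectomy | Directly before the DE-CBCT |
| 3.III, day 1 | Same day; typically neCT and mCTA/CTA | None |

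**Step 2. Section 8.8.2.** The only named references are mCTA and CTP, and Section 6.5 schedules them only on admission. For 3.II every available pair therefore straddles thrombectomy, and choosing between the two named references does not change that. Section 5.5 itself expects change by day 2, since it justifies the second 3.I scan as information on stroke progression. The documents give no figure for how much penumbra remains on day 2, so this part cannot be sized.

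**Step 3. Section 8.8.4.** Two readings are open.

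- *Admission CT.* Table 3 labels day-1 imaging CT-based and day-2 imaging DECT, and Section 8.8.4 lists CT and DECT separately. Both favor this reading.
- *Day-2 DECT.* Section 6.2.1 counts DECT as CT for comparison, and Section 8.8.4 allows it as reference.

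**Step 4. Illustration under the admission reading.** Inputs:

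- R, the share of 3.II subjects recanalized. Section 2.11.2 cites "better 24-h recanalization rates (71% of successful recanalization rate"), so R = 0.71. This comes from earlier thrombectomy trials, not from this study.
- f, the share of 3.II among applicable subjects. The documents do not give it, so it is varied.
- A recanalized artery is assumed to hold no thrombus, and the device is assumed perfect.

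Highest possible match within 3.II = 1 − R = 1 − 0.71 = 0.29. If R were 0.50 or 0.90 (assumed range), it would be 0.50 or 0.10.

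Highest possible match over all applicable subjects = 1 − R × f. With R = 0.71:

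| f | 1 − 0.71 × f |
|---|---|
| 0.25 | 0.82 |
| 0.50 | 0.65 |
| 0.75 | 0.47 |

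More than half of all targets are lost only if f exceeds 0.50 / 0.71 = 0.70.

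**Step 5. Same inputs under the day-2 reading.** The DECT directly precedes the DE-CBCT, so the loss from timing is about zero. On the same illustration, about 29% of 3.II subjects with an admission thrombus would still have one to assess.

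**Step 6. Section 8.8.6.** For 3.II the concurrent scan is the DECT. A clot absent from both scans counts as agreement, so the thrombus item is not harmed. Tissue at risk is different, because no perfusion scan is scheduled on day 2 to define it.

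**The case against.** The strongest defense has four parts.

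- **Status.** None of these objectives has a hypothesis, sample size or success threshold, and Sections 8.8.2 and 8.8.6 are labeled exploratory. This stands, and it sets the severity.
- **The thrombus reference may already be right.** Section 8.8.4 allows DECT, and the 3.II DE-CBCT directly follows one. A reader might infer that no choice of reference could help, because treatment has removed the target. The documents do not support that for Sections 8.8.4 and 8.8.6: with the day-2 DECT the problem goes away. What remains in Section 8.8.4 is an unstated time point. The defense does not reach Section 8.8.2, where DECT is not a named reference.
- **No detection rate is defined.** A reader might infer that a removed clot would be scored as a device failure. Section 8.8.4 lists descriptors and a comparative rating, and Section 8.1 gives readers both image sets together for such ratings. So the 29% is a ceiling on an illustrative match rate, not on a planned endpoint. Still, no category is listed for a target that is no longer present, so pooled ratings would be hard to interpret.
- **The remedy is not perfectly clean.** 3.I subjects may receive thrombolysis, and its timing relative to the day-1 DE-CBCT is not given. That stands as a limitation, although the day-1 pair is still the closest in time to admission imaging.

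Three other strong readings also fail. Thrombus is not to be characterized in all ischemic subjects, only in those with one on CT. Group 3.II is defined by having been subjected to thrombectomy (Section 6.6.3.1), so not every clot is gone. And the documents do not show that a perfect device would miss most targets overall: that needs f above 0.70, and the split between 3.I and 3.II is not stated.

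**Conclusion.** The point holds firmly for Section 8.8.2. As written, penumbra and collateral score in 3.II are compared across thrombectomy, and disagreement cannot be attributed to the device. Its size is not quantifiable from the documents.

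For Section 8.8.4 it holds conditionally. If the admission CT is the reference, about 29% of admission thrombi within 3.II could be matched at best. This rests on the cited 71% applying here and on recanalization meaning that no thrombus is left. If the day-2 DECT is the reference, there is no mismatch but few 3.II subjects qualify. For Section 8.8.6 only the tissue-at-risk item is affected.

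Severity is minor. The primary and secondary endpoints are outside this point.

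**What to change.** Name the paired reference scan by group.

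- **Section 8.8.2:** restrict the penumbra and collateral-score comparison with admission mCTA/CTP to the day-1 DE-CBCT of 3.I subjects. Report any 3.II infarct volume separately and descriptively.
- **Section 8.8.4:** pair each DE-CBCT with the scan nearest in time, meaning the admission CT/CTA for 3.I day 1 and the day-2 DECT for 3.II. Include 3.II subjects only if that DECT shows residual thrombus. Use mTICI, which is already recorded, only to describe them: it is an angiographic score and cannot serve as reference for thrombus attenuation or size.
- **Section 8.8.6:** limit the tissue-at-risk item to 3.I day-1 scans. Keep 3.III as negative controls for infarct and thrombus, where they can reveal false-positive segmentation.

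No new scan or data item is needed. The cost is fewer subjects for these additional objectives.
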